10. SAFETY

10.1 Drug studies

Not applicable

10.2 Medical Device Category C studies

Not applicable

10.3 Medical Device Category A studies

Not applicable

10.4 Other clinical trial Category B

During the entire duration of the study, all adverse events (AE) and all serious adverse events (SAEs) are collected, fully investigated and documented in source documents and case report forms (eCRF). Study duration encompassed the time from when the participant signs the informed consent form until the last protocol-specific procedure has been completed.

10.4.1 Definition and assessment of (serious) adverse events

An **AE** is any untoward medical occurrence in participant administered an intervention a clinical investigation and which does not necessarily have a causal relationship with the intervention. An AE can therefore be any unfavourable and unintended sign (including an abnormal laboratory finding), symptom, or disease temporally associated with the intervention, whether or not related to the intervention. [ICH E6 1.2, adapted]

A **SAE** is classified as any event which:

- requires inpatient treatment of at least 24 hours or extends a current hospital stay;
- results in permanent or significant incapacity or disability;
- is life-threatening or results in death; or
- causes a congenital anomaly or birth defect.

In addition, important medical events that may not be immediately life-threatening or result in death, or require hospitalisation (regardless of the duration of the hospitalization), but may jeopardise the patient or may require intervention to prevent one of the other outcomes listed above should also usually be considered serious.

A hospitalisation or a prolongation of a current hospitalisation for a diagnostic or elective (surgical) procedure that was already planned prior to the participant's enrolment into the study is not classified as an SAE.

SAEs should be followed until resolution or stabilisation. Participants with ongoing SAEs at study termination will be further followed up until recovery or until stabilisation of the disease after termination, or until the participant is lost to follow-up.

Assessment of Causality

The assessment of causality of SAEs will be done by both, investigator and Sponsor based on the criteria listed in the ICH E2A guidelines below. For events of special interest (all SAEs, respiratory events, cardiovascular events, AEs with prescription of systemic antibiotics and AEs for which a causal relationship between the AE and vaping or smoking is not excluded) a smoking assessment questionnaire will be filled out in relationship to the event to facilitate the assessment of causality.

Relationship	Description
Definitely	Temporal relationship Improvement after dechallenge* Recurrence after rechallenge (or other proof of drug cause)
Probably	Temporal relationship Improvement after dechallenge No other cause evident
Possibly	Temporal relationship Other cause possible
Unlikely	Any assessable reaction that does not fulfil the above conditions
Not related	Causal relationship can be ruled out
*Improvement after dechallenge only taken into consideration, if applicable to reaction	

Assessment of Severity

Classification and severity grading scale in this study will be performed in accordance with “Common Terminology Criteria for Adverse Events CTCAE Version 5 terminology.

Document collection for (S)AE adjudication

(S)AE Guidelines have been established to ensure complete document collection by the sites to allow proper adjudication by the adjudication committee for all SAEs and specific AEs (important cardiovascular events, important respiratory events, new cancer diagnosis and AE with at least possible relationship to vaping).

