1.7 Any other relevant Committee, Person, Organisation, Institution

Data management

CTU Bern, Faculty of Medicine, University of Bern,
[name], [name], Switzerland, [contact]

Study Steering Committee

The study steering committee will be responsible for the overall supervision of the trial and will regularly meet to discuss scientific and logistic aspects of the trial. The study steering committee consists of 7 persons, at least one person from each center involved in the study.

Data and Safety monitoring board

A committee of clinical research experts and patient advocates who monitor the progress of the clinical trial and review safety and effectiveness data while the trial is ongoing will be formed. This committee is independent of the people, organizations, and institutions conducting the clinical trial. The committee can recommend that the trial is stopped early because of concerns about participant safety.

Adjudication Committee

The adjudication committee is an independent group of experts that reviews serious adverse events and adverse events of interest in order to give expert opinions about clinical safety.

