6.2.3 Other methods of minimising bias

To minimize bias of safety outcomes, all clinical events (hospitalizations) and other serious adverse events will be verified by a blinded external committee whenever possible (see 1.7.3).

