11.4.5 Safety analysis

We will compare the proportion of adverse events and serious adverse events between groups using recommended methods.

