2.8 Blinding

Participants, nurses and investigators will not be blinded. The laboratory personnel will be blinded for the determination of all urinary metabolites of nicotine (anabasine, cotinine, nornicotine, 3-OH cotinine). Any adverse event occurred in this study that generated care by a physician will be verified by a blinded external committee whenever possible. ~~The statistician who authors this SAP and performs the blinded~~

CTU Bern	SAP for: ESTxENDS	Version: 1-02.0
----------	-------------------	---------------------------------

CTU Bern	Template: Statistical Analysis Plan (SAP)	Version: 03	
	Code: CS_STA_TEM-11	Valid from: 28-02-2019 5.6.2023	Page 7 of 27

~~primary ITT and secondary per-protocol analysis of the primary and secondary smoking cessation outcomes will be blinded.~~ All ~~other~~ statisticians and data managers will not be blinded. The laboratory personnel will not be blinded for further urinary measures of exposures such as metabolites of polycyclic aromatic hydrocarbons (PAHs), of VOCs, creatinine and metabolites of TSNAs (NNAL, NNN, NNK).

There will be an automatic import of these urinary lab values into the database, programmed by a CTU data manager. Specific procedure and time points will be defined.

~~Breaking the blind:~~

~~The blinded statistician will be unblinded when all outcomes with blinding of the primary analysis are completely analysed. An unblinded statistician will have to download and label the data and prepare the analysis sets for the blinded analysis.~~

CTU Bern	SAP for: ESTxENDS	Version: 1.02.0	
CTU Bern	Template: Statistical Analysis Plan (SAP)	Version: 03	
	Code: CS_STA_TEM-11	Valid from: 28.02.2019 5.6.2023	Page 8 of 27

3. Data management

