- Number of cigarettes smoked per day (CPD), self-reported, at baseline, TQD, phone visits and 6 months visit
- Change in number of cigarettes smoked per day (CPD), self-reported. Successful reduction defined as 50% reduction in CPD.
- Respiratory symptoms assessed by questionnaires:
 - Change in COPD Assessment Test (CAT) from baseline to month 6, score from 0-40 (regarded as continuous)
- Change in cardiovascular risk factors from baseline to month 6, assessed by
 - Total cholesterol (continuous)
 - HDL-cholesterol (continuous),
 - LDL-cholesterol (calculated, continuous),
 - triglycerides (continuous),
 - blood pressure levels (continuous),
 - heart rate (continuous),
 - waist circumference (continuous) and
 - body mass index (continuous).
- AEs (in categories from adjudication committee)
- SAEs (in categories from adjudication committee)

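### One trigger for adjudicating non-serious AEs is possible relation to vaping, with no smoking counterpart; it conflicts with SAP 2.8 and can tilt the committee-categorised AE outcome against the ENDS arm

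*Supplement*

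**What the plan says.** The latest protocol (9.0) and SAP (2.0) describe the scope of adjudication in four places.

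- **Protocol 10.4.1, document collection for (S)AE adjudication:** all SAEs, and specific AEs, namely important cardiovascular events and "important respiratory events, new cancer diagnosis and AE with at least possible relationship to vaping".
- **Protocol 6.2.3:** "all clinical events (hospitalizations) and other serious adverse events will be verified by a blinded external committee whenever possible".
- **Protocol 1.7:** the committee "reviews serious adverse events and adverse events of interest in order to give expert opinions about clinical safety". That section does not define the AEs of interest.
- **SAP 2.8:** "Any adverse event occurred in this study that generated care by a physician will be verified by a blinded external committee whenever possible".

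Three further texts bear on the point. A little earlier in 10.4.1, the smoking assessment questionnaire is required for, among others, "AEs for which a causal relationship between the AE and vaping or smoking is not excluded", so that rule covers both products. The causality scale in 10.4.1 describes the level of a possible relation as "Temporal relationship Other cause possible". SAP 6.1 lists "AEs (in categories from adjudication committee") among the core secondary outcomes, and SAP 4.3.1 says secondary outcomes are analysed by randomised group.

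**The concern.** An AE that never reaches the committee cannot have a committee category. The selection rule therefore decides which non-serious AEs can enter the SAP 6.1 outcome, unless the SAP says otherwise, and it does not.

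Three features of the vaping trigger make it a poor selection rule for a comparison between arms. It names one product only. Its threshold is low, since on the protocol's scale a temporal relationship suffices even when another cause is possible. It is applied by sites that know the allocation and the product used. A headache in a participant who vapes can qualify by this route, and the same headache in a control participant who only smokes cannot. An apparent excess of adjudicated AEs with ENDS could then be a product of the rule.

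The safeguards around this outcome also matter more in the latest SAP, because version 2.0 makes all statistical analyses unblinded.

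**Working it through.** **Inputs from the documents.** Protocol Table 11.2-1, 6 months:

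- Intervention arm, ENDS users: 56 + 111 = 167, of 56 + 111 + 50 + 340 = 557 followed up; 167/557 = 30.0%.
- Control arm, ENDS users: 11 + 17 = 28, of 11 + 17 + 56 + 473 = 557; 28/557 = 5.0%.

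This reproduces the 30% and 5% stated in protocol 11.2. The ratio of users is 167/28 = 6.0. Planned size is 586 per arm.

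**Inputs assumed, because the documents give no figure**, each equal in both arms:

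- a, share of participants with any AE: 20% to 40%.
- t, share of those caught by triggers that refer to no product: 10% to 30%.
- q, probability that an AE in an ENDS user is rated at least possibly related to vaping: 10% to 60%.

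**Model with no true effect.** With u the share using ENDS, the share of participants with an adjudicated AE is

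p = a × [t + (1 − t) × u × q].

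In the ratio between arms, a cancels:

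RR = [t + (1 − t) × 0.30 × q] / [t + (1 − t) × 0.05 × q].

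| Case | Intervention bracket | Control bracket | RR |
|---|---|---|---|
| t = 0.3, q = 0.1 | 0.3 + 0.7 × 0.30 × 0.1 = 0.3210 | 0.3 + 0.7 × 0.05 × 0.1 = 0.3035 | 1.06 |
| t = 0.1, q = 0.3 | 0.1 + 0.9 × 0.30 × 0.3 = 0.1810 | 0.1 + 0.9 × 0.05 × 0.3 = 0.1135 | 1.59 |
| t = 0.1, q = 0.6 | 0.1 + 0.9 × 0.30 × 0.6 = 0.2620 | 0.1 + 0.9 × 0.05 × 0.6 = 0.1270 | 2.06 |

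In the middle row with a = 40%, the expected numbers are 586 × 0.4 × 0.1810 = 42 and 586 × 0.4 × 0.1135 = 27 participants. A test at the nominal 5% level would then show an excess with probability about 0.50. Over the whole grid that probability runs from about 0.04 to 0.93.

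The 30% is use at 6 months. Use at any time in the intervention arm may be higher, but the documents give no figure. If it were 80%, an assumption, the ratio would run from 1.17 to 4.19.

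**With an arm-neutral rule** the term in u disappears and the null ratio is 1.0.

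**What a file sent only under the vaping trigger would suggest.** At equal AE and rating rates among users, the probability that it comes from the intervention arm is 0.30/(0.30 + 0.05) = 86%.

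**The case against.** Much of the case on the other side stands, and it limits the point.

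- **A certain excess.** A reader might infer that the outcome will show one. The documents do not support that. The list in 10.4.1 sits in a paragraph on collecting documents and does not define an outcome. SAP 6.1 may mean only that AEs are sorted by the committee's category scheme, and SAP 2.8 gives a rule without the asymmetry. The excess is conditional on counting what 10.4.1 selects.
- **A doubling.** Suppose a 20% AE risk in ENDS users, every such AE rated possible, and 20 neutral events per arm. That gives (20 + 0.2 × 167)/(20 + 0.2 × 28) = 53.4/25.6 = 2.1. With 100 neutral events per arm it is 133.4/105.6 = 1.26. The doubling is a high-end case.
- **Bias in the whole safety comparison.** This does not follow either. All AEs are collected in both arms, and the any-AE and any-SAE summary in SAP 6.6 does not depend on adjudication. Protocol 11.4.5 ("We will compare the proportion of adverse events and serious adverse events between groups using recommended methods") does not mention it. All SAEs go to the committee, and the cardiovascular, respiratory and cancer triggers name no product. SAP 6.6 also stratifies AEs by consumption, which helps a reader see where product use drives counts.
- **A trigger that only the ENDS arm can meet.** It follows use, not arm; 5% of controls are expected to vape.
- **An unmasked committee.** The documents do not say that it sees the reason for selection, the site's causality rating or the questionnaire. The (S)AE guidelines are not part of the supplement. Blinding is promised only where possible, and product use is not allocation.
- **Almost every AE in a vaper qualifying.** The causality table is introduced for SAEs, and sites may rate lower. This is why q is shown as a range.

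None of this removes the one-sided trigger or the conflict between the four statements of scope. The table of changes in SAP section 7 does not mention that conflict.

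**Conclusion.** The point holds in a conditional form. The protocol's selection rule for non-serious AEs is one-sided and disagrees with SAP 2.8, and protocol 6.2.3 and 1.7 give two further scopes. If the SAP 6.1 outcome counts AEs selected under 10.4.1, a ratio above 1 is expected with no true effect. At the documents' 30% versus 5% ENDS use it is about 1.06 to 2.06, depending on the assumed values of t and q. The effect is confined to non-serious AEs outside the cardiovascular, respiratory and cancer classes. The risk to masking is confined to files sent solely under the vaping trigger, and arises only if the committee is shown why they were sent. The primary outcome is not touched. This should be corrected because it concerns a declared secondary safety outcome and the correction is cheap.

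**What to change.** 1. State one arm-neutral adjudication rule in protocol 10.4.1 and SAP 2.8 and 6.1, and bring protocol 1.7 and 6.2.3 into line with it.
2. Say in SAP 6.1 which AEs the outcome counts. Restrict between-arm counts of committee-categorised AEs to those meeting arm-neutral triggers: SAEs, important cardiovascular, important respiratory and new cancer events, and physician-treated AEs if the SAP 2.8 rule is kept.
3. List AEs adjudicated solely for possible relation to vaping separately, outside those counts.
4. Have the committee assign category and grade before product use or the site's causality rating is shown, and judge relation to vaping afterwards.

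The cost is wording, a little administration for preparing files, and fewer AEs in the adjudicated comparison. The minimum version, leaving AEs adjudicated solely for vaping out of the arm comparison, is analysis work only.

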10.4.2 Reporting of serious adverse events (SAE) and other safety related events

Reporting of SAEs

All SAEs for which it cannot be excluded that the events are attributable to the study intervention will be reported immediately and within a maximum of 24 hours of learning of its occurrence to the Sponsor of the study. Reporting is done via the eCRF which generates an automatic email notification to the Sponsor once an SAE is entered (and saved) in the system. In addition these events are also reported by the Sponsor to the CEC and local ECs (as applicable) within 15 days.

Reporting of safety and protective measures

If immediate safety and protective measures have to be taken during the conduct of the trial, the investigator notifies the CEC of these measures, and of the circumstances necessitating them, within 7 days. The Sponsor must immediately inform all participating Investigators about all safety and protective measures. The other in the trial involved Ethics Committees will be informed about safety and protective measures via the Sponsor.

Periodic reporting of safety

An annual safety report is submitted by the Sponsor once a year to the responsible Ethics committees and is also provided to all participating Investigators.

11. STATISTICAL METHODS

11.1 Hypothesis

The primary hypothesis of this trial is that providing smokers with ENDS and SOC leads to a higher rate of smokers with continuous smoking cessation from target quit date than SOC alone.

11.2 Determination of Sample Size

Primary outcome:

Sample size calculation of the ESTxENDS trial at 6 months follow-up: Based on the results of a systematic review and meta-analysis of previous trials, we expect an RR of smoking cessation of 1.6. Based on our previous RCTs, we expect a 12% quit rate in the control group and a 19% quit rate in the intervention group (ENDS + SOC) (7% absolute difference in continuous abstinence rate from target quit date [TQD]) for the main outcome in ESTxENDS at 6 months. With a two-sided alpha of 0.05 and a power of 90%, we therefore planned to include a minimum 557 smokers per group, for a total of 1,114 smokers, to find a significant difference in quit rates. Previous experience suggests we should assume a 5% loss to follow-up, so we increased our sample size by 5% (59 smokers). We will thus recruit 1,172 smokers. Though participants in the control group will not be actively provided with ENDS and asked not to use ENDS during the first 6 months of the study, we expect that 5% will still purchase ENDS on their own. The sample size of the entire trial is based on the primary outcome; the power to find a statistically significant difference for secondary outcomes is limited to the total number of participants.

Estimated power to detect significant differences in groups on smoking cessation at 12- and 24-months follow-up: Assuming 10% will have quit smoking in the control group at 12 months (continuous smoking cessation rate from TQD), and applying the RR of 1.6, we estimate 16% will have quit in the intervention group. Assuming 7% loss to follow-up, we will have 86% power to detect such a difference. Based on the literature and previous experience in our own trials,^{133, 163} we expect a 10% relative increase in absolute smoking cessation rate by choosing 7-days point prevalence as the main outcome with no change in RR estimate.¹⁶³ We will have 90% power to detect a significant difference by choosing the 7-days point prevalence as a main outcome for the 12-months follow-up. We thus expect an 11% quit rate in the control group and 17% in the intervention group at the 12-month follow-up (6% absolute difference). At the 24-month follow-up, we can expect 8% in the control group will have stopped smoking and 12% in the intervention group. Assuming a 10% loss to follow-up rate, we will have 62% power to detect a significant difference between groups.

Secondary outcomes: The sample size of the entire trial is based on the primary outcome; the power to find a statistically significant difference for secondary outcome is limited to the total number of participants. For safety outcomes, we do not expect to find statistically different results between groups on SAEs. For toxicological outcomes of ENDS, such as measures of urinary biomarkers, we will compare participants based on ENDS exposure. Table 11.2-1 presents the number of participants we expect to fall into each category of ENDS and cigarette smoking over follow-up. In the intervention group, we expect that 19% of smokers would quit and 30% would use of ENDS at the 6-month follow-up.⁹ In the control group, we expect that 12% of smokers who quit at 6-month follow-up. Though participants in the control group will not be actively provided with ENDS during the first 6 months of the study, we expect 5% will purchase ENDS on their own.

Table 11.2-1: Expected distribution of participants over follow-up

Group	Intervention group					Control group					Legend:
	Ai	Bi	Ci	Di	Ei	Ac	Bc	Cc	Dc	Ec	
ENDS	+	+	-	-		+	+	-	-		Ai= ENDS use, stop smoking, intervention
Tob smk	-	+	-	+		-	+	-	+		Bi= ENDS use, smoking, intervention
Baseline		586							586		Ci= No ENDS, stop smoking, intervention
											Di= No ENDS, smoking, intervention
											Ei= Lost to follow-up (LTFU), intervention
6 months: N	56	111	50	340	29	11	17	56	473	29	Ac= ENDS use, stop smoking, control
% of group	10%	20%	9%	61%	5%	2%	3%	10%	85%	5%	Bc= ENDS use, smoking, control
12 months: N	49	93	38	365	41	11	16	44	474	41	Cc= No ENDS, stop smoking, control
% of group	9%	17%	7%	67%	7%	2%	3%	8%	87%	7%	Dc= No ENDS, smoking, control
24 months: N	37	79	32	380	59	11	16	26	475	59	Ec= LTFU, control
% of group	7%	15%	6%	72%	10%	2%	3%	5%	90%	10%	

For measures of carcinogenicity, such as measures of incomplete combustion agents (VOCs and PAH: 1-OHP, 1- and 2-NAPH in urine)^{29,30} and exposure to TNSAs (NNK and NNN in urine),¹⁸ and measures of oxidative stress in urine (8-OHdG and 8-isoprostane),^{41, 91, 164} and MN in buccal epithelium, we will compare groups that stopped smoking with or without ENDS in intention to treat analyses (Ai+Ci vs. Ac+Cc; 112 vs. 70) and in per protocol analyses (Ai+Ac vs. Ci+Cc; 65 vs. 117). Based on previous cross sectional studies contrasting past smokers to smokers,^{52, 164, 165} we estimate a 48% power to detect significant differences between quitters and continuing smokers for 8-OHdG and 100% for 8-isoprostane between baseline and follow-up, at alpha 0.05 and an assumed correlation between baseline and follow-up of 0.7 (Table 11.2-2). We will perform 3 determinations of buccal MN on 2000 cells for each participant. Based on published results,^{99, 100, 166-168} we expect a baseline frequency among non-smokers of 0.74 MNs per thousand cells and a between-subject GSD of 1.3. We will have 80% power to detect a significant difference between smokers and non-smokers for a frequency ratio (FR) of 1.5.

For the 6-months changes in cardiovascular risk factors, we do not have direct data from RCT of ENDS use. Using data from previous RCT on nicotine replacement therapy, we expect a mean increase in HDL-cholesterol of 0.107 mmol/l (95% confidence interval 0.057 to 0.158 mmol/l) among quitters,⁵⁴ an increase in systolic blood pressure of 1.65 mm Hg and in diastolic blood pressure of 0.90 mm Hg after 6 months in quitters.^{55, 56} Considering data from the CoLaus study, a study on cardiovascular risk factors in a random sample of the Lausanne population, we expect to only have a 10 to 40% chance to detect a difference between ENDS users and continuing smokers.¹⁶⁹ We expect to be able to have 100% power to detect changes in respiratory symptoms.^{8, 170}

We do not expect to have adequate power to detect changes in incidence of cancer. However, we will apply strict open access rules and post the data on rigorous and systematic assessment of self-reported cancer in an online repository to enable the international community to pool results with other datasets and answer more definite answers on these important outcomes

Table 11.2-2: Power calculation and sample size required to detect statistically significant differences between past- and current smokers for secondary outcome measures

Measure	Matrix	Non smoker	Past smoker	Current smoker	Reference	Power * N **	
		Mean (SD)	Mean (SD)	Mean (SD)			
Inhaled compounds							
1-OHP	Urine [µg/g creat]	0.08 (0.11)	0.11 (0.11)	0.2 (0.25)	Bartolomé et al. 2015 ¹⁷¹	98%	37
	Urine [µg/g creat]		0.04 (0.002)	0.12 (0.005)	Naufal et al. 2011 ¹⁷²	100%	2
1-naphtol	Urine [ng/g creat]		1.6 (0.1)	7.2 (0.4)	Naufal et al. 2011 ¹⁷²	100%	2
2-naphtol	Urine [ng/g creat]		1.8 (0.05)	8.9 (0.5)	Naufal et al. 2011 ¹⁷²	100%	2
Oxydative stress							
8OHdG	Urine [ng/mg creat]	2.75 (1.6)	3.62 (2.41)	4.24 (3.3)	Sauvain et al., 2011 ¹⁶⁴	48%	174
	EBC [ng/ml]	0.36 (0.09)	0.31 (0.10)	0.52 (0.15)	Doruk et al., 2011 ⁹¹	100%	3
8-isoprostane F2a	Urine [µg/g creat]	0.51 (0.04)	0.74 (0.07)	1.1 (0.1)	Harman et al., 2003 ⁵²	100%	2
	Urine [µg/g creat]	0.7 (2.7)		4.48 (2.7)	Seet et al., 2011 ⁴³	100% [†]	5
	EBC [pg/ml]	10.8 (0.8)		24.3 (2.6)	Montuschi et al., 2000 ⁸⁹	100% [†]	2

*Power to detect statistically significant difference between quitters (past smokers) and continuing smokers (current smokers) between baseline and follow-up at alpha 0.05, an assumed correlation between baseline and follow-up of 0.7 and 182 participants (112 vs. 70) for urine analyses.

† Calculations above in * based on data from never smokers compared to current smokers.

** Number of participants per group needed to detect statistically significant differences at alpha of 0.05 and beta (power) of 0.80.

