Micronuclei assessment in buccal epithelium, a surrogate measure of future cancer risk, will be done at baseline, and at the 6-, 12- and 24-months follow-up visits. Buccal cells will be harvested with a cytobrush. Participants will harvest their own cells by rotating the cytobrush on the inner cheeks of the mouth. The cytobrushes will be transferred or mailed to the laboratory in a buffer. The buccal cells will then be centrifuged, separated mechanically with tissue homogenizer, filtered, transferred onto microscope slides and left to air dry. The cells will be fixed in ethanol/glacial acetic acid and stained with DAPI (4',6-diamidino-2-phenylindole). An automatic MN counting system will be applied. MN frequency will be calculated as number of cells that contain MNs divided by the total number counted. A minimum of 1000 cells will be counted per participant.

The olfactory function will be assessed at baseline and at the 6-, 12- and 24-months follow-up visits by using the Burghart Sniffin' Sticks 16-item Identification-test.^{110-112, 154} The participants will be asked to not have eaten, drunk anything but water, smoked, used ENDS or chewed gum for at least 15 minutes before the olfactory function test. 16 commonly known odours will be presented to the participants for around 3-4s each, after which the participants will be asked to select the correct answer from 4 possible answers (forced choice). The highest possible score olfactory identification score (OIS) is 16; the cut-off for hyposmia is 11 points and cut-off for anosmia is 8 points. This will be performed at baseline and at the 6-, 12- and 24-months follow-up visits.

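### The 12- and 24-month powers in protocol section 11.2 leave out the loss to follow-up they are said to assume, and the biomarker powers are computed with group sizes from a different comparison

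*Supplement*

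**What the plan says.** All references are to protocol version 9.0.

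- **12 months, continuous abstinence (11.2).** The rates are 10% in the control arm and, applying a relative risk of 1.6, 16% in the ENDS arm. "Assuming 7% loss to follow-up, we will have 86% power to detect such a difference".
- **12 months, 7-day point prevalence (11.2).** This is the primary outcome at that visit (5.1). Cessation rates are taken to rise by a relative 10% with the relative risk unchanged. "We will have 90% power to detect a significant difference by choosing the 7-days point prevalence as a main outcome for the 12-months follow-up". The next sentence reads "We thus expect an 11% quit rate in the control group and 17% in the intervention group at the 12-month follow-up (6% absolute difference").
- **24 months (11.2).** The text expects 8% v 12%. "Assuming a 10% loss to follow-up rate, we will have 62% power to detect a significant difference between groups".
- **Table 11.2-1** has a separate lost-to-follow-up column (41 per arm at 12 months, 59 at 24 months) and expected numbers in each smoking and ENDS category.
- **Urinary markers (11.2).** "we estimate a 48% power to detect significant differences between quitters and continuing smokers for 8-OHdG". The footnote to Table 11.2-2 bases this on "182 participants (112 vs. 70) for urine analyses", with a baseline to follow-up correlation of 0.7. The text above the table defines 112 v 70 as Ai+Ci v Ac+Cc.
- **Losses (11.5)** are counted as persistent smokers in the intention-to-treat analysis.

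**The concern.** A power figure quoted with a loss rate should reflect that loss, and one quoted for a contrast should use the sizes of the groups in that contrast. Neither holds here. The 12-month text also gives two versions of the intervention rate, and the 24-month text and table give different rates for the same visit.

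These are the protocol's only power statements for the primary outcomes of the extension and for the oxidative-stress markers. A reader would rate the 12- and 24-month comparisons somewhat too highly. The same reader would think the 8-OHdG contrast close to even odds of detection when, as described, it is well powered.

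**Working it through.** **Binary outcomes.** Two-sided alpha 0.05, n per arm, pooled variance under the null:

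Power = Φ{ [ |p2 − p1|·√n − 1.96·√(2p̄(1 − p̄)) ] / √(p1(1 − p1) + p2(1 − p2)) }, with p̄ = (p1 + p2)/2.

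Inputs are the rates in 11.2, 586 randomised per arm (6.1), 586 × 0.93 = 545 followed at 12 months, and 586 × 0.90 = 527 at 24 months.

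Worked case, 10% v 16%. The null term is 1.96 × 0.4756 = 0.932 and the denominator is 0.4737.
- n = 586: (0.06 × 24.21 − 0.932)/0.4737 = 1.098, power 86.4%. This is the stated 86%.
- n = 545: (0.06 × 23.35 − 0.932)/0.4737 = 0.989, power 83.9%.

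| Comparison | Stated | No loss (586) | Loss applied | All 586, lost = smoker |
|---|---|---|---|---|
| 12 mo, 10% v 16% | 86% | 86.4% | 83.9% | 83.5% |
| 12 mo, 11% v 17.6% | 90% | 89.9% | 87.6% | 87.3% |
| 12 mo, 11% v 17% | 90% | 84.2% | 81.5% | 81.1% |
| 24 mo, 8% v 12% | 62% | 62.7% | 58.1% | 57.7% |

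All three stated figures match the no-loss column. The 90% also needs 17.6%, which is 11% × 1.6 and also 16% × 1.1. The printed 17% does not give 90% even with no loss.

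**Could the rates already be net of loss?** Table 11.2-1 rules this out, because it applies the rates to completers. At 12 months, (49 + 38)/545 = 16% and (11 + 44)/545 = 10%.

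**24 months, table against text.** The table has 37 + 32 = 69 ENDS-arm quitters and 11 + 26 = 37 control quitters. With 586 − 59 = 527 completers per arm, that is 13.1% v 7.0%. The formula then gives 90.7%, against 58.1% on the text's rates.

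**8-OHdG.** Inputs from Table 11.2-2: past smokers 3.62 (SD 2.41), current smokers 4.24 (SD 3.3), difference 0.62. The variance factor is 1 − 0.7² = 0.51.

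SE = √[0.51 × (2.41²/n_past + 3.3²/n_current)]; power = Φ(0.62/SE − 1.96).

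- Plan's figure, 112 past and 70 current: SE = 0.325, ratio 1.906, power 47.9% (stated 48%).
- Plan's N for 80% power: (1.96 + 0.842)² × 0.51 × (2.41² + 3.3²)/0.62² = 173.9 (stated 174).
- 1-OHP (0.11, SD 0.11 v 0.20, SD 0.25) at 112 and 70: 98% (stated 98%).

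So 112 was entered as the past-smoker group and 70 as the current-smoker group, yet all 182 are quitters by the protocol's own definition. The current Table 11.2-1 gives 56 + 50 = 106 and 11 + 56 = 67 quitters at 6 months, so 112 and 70 are also out of date.

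For the contrast named, the same table gives 106 + 67 = 173 quitters and (111 + 340) + (17 + 473) = 941 continuing smokers. Then SE = 0.152, ratio 4.086, power 98.3%. With change-score variance, factor 2(1 − 0.7) = 0.6, power is 96%. 1-OHP rises to 100%, and the markers already at 100% stay there.

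**6-month sample size.** 12% v 19% at 90% power needs 560 per arm by the same approach, against 557 stated, so it is in order.

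**The case against.** The strongest reply concerns the 12-month 90%. The text derives the point-prevalence rates with an unchanged relative risk, which leads to 17.6%; the printed 17% then looks like a rounding slip. On that reading the omitted loss costs about 2 points. This stands. A reader might infer that the true power is simply 82%, but the text does not support that as the sole correction: 82% follows only from the printed 17%. Restating 84% for continuous abstinence and 82% for point prevalence would also contradict the plan's reason for choosing point prevalence, which is that it raises power. It is also fair that the 90% sentence names no loss rate; the 7% carries over from the sentences before it.

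A reader might infer that the extension was justified on these figures. The history of changes attributes it to additional funding. The SAP excludes the 12- and 24-month outcomes, so no analysis rule there depends on them.

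A reader might also add the micronucleus count, since 11.2 says "We will perform 3 determinations of buccal MN on 2000 cells for each participant" and 9.2.2 says "A minimum of 1000 cells will be counted per participant". A minimum does not contradict a larger target, and the 80% power claim gives no group size against which to test it.

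Finally, the marker error understates power and materially changes only 8-OHdG, and results are to be reported with confidence intervals. That limits the harm but does not make the stated figure right.

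**Conclusion.** The point holds as an error in stated figures. With the assumed losses applied, the 12-month continuous-abstinence power is 84%, not 86%, and the 24-month power on the text's rates is 58%, not 62%. The 12-month point-prevalence power is about 88% or 82%, depending on which of the plan's two intervention rates is meant; neither gives 90%. The largest ambiguity is at 24 months, where text and table imply 58% and about 91%.

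For quitters v continuing smokers, 8-OHdG power is about 98% (96% with change-score variance), not 48%. This rests on the plan's cited means and SDs, the correlation of 0.7, and urine being measured in all completers. It says nothing about power to compare quitters between arms, for which a past-v-current-smoker difference is not the relevant effect.

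The 6-month sample size and the total of 1172 are unaffected.

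**What to change.** In section 11.2:

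1. Restate the 12-month continuous-abstinence power as 84%.
2. Reconcile the 17% with the unchanged relative risk of 1.6, and give the matching power: about 88% for 11% v 17.6%, or 82% if 11% v 17% is meant.
3. Align the 24-month rates in the text and Table 11.2-1. State 58% if 8% v 12% is kept, or about 91% if the table's 13% v 7% is intended.
4. Recompute the urine rows of Table 11.2-2 with about 173 quitters v 941 continuing smokers, and say that this assumes all completers are measured. Update 112 v 70 to 106 v 67 where quitters are compared by arm, and do not quote the table's powers for that comparison.

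The cost is protocol text only, with no added participants, visits or assays. The 12-month figures and the text's 24-month figure become slightly less favourable, and the 8-OHdG figure much more so.
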